8.4.3. Reporting of Pregnancy

While pregnancy itself is not considered an AE, pregnancy occurring in a clinical study must be followed to collect information regarding the experiences of gestation and pregnancy with study device exposure. The investigator must report any pregnancy that occurs in a female study subject or female partner of a male subject subsequent to first exposure to the study device until EOS, or within 3 months following a subject's last use of the device in the event of early termination. All pregnancies will be reported to the IRB, Sponsor, and CRO. In the event of a pregnancy, treatment will be discontinued, and the subject will undergo continued safety follow-up through pregnancy outcome.

Any pregnancy must be followed by the investigator until delivery or to the end of pregnancy. Any anomalies, complications, abnormal outcomes, or birth defect(s) observed in the child must be reported as an SAE within 24 hours of the investigator or study personnel's first knowledge.

8.5. Study Halting Rules

If any of the following safety events occur, a Safety Evaluation Meeting (defined below) will be triggered:

- Three or more SAEs (including SADEs and UADEs) that are assessed as possibly or definitely related to the study device by an investigator and confirmed as such by the Sponsor (see Section 8.2.2).
- An overall pattern of symptomatic, clinical, or laboratory events associated with the study device that the Sponsor's Program Physician or designee consider a serious potential safety concern (e.g., suspicious overall pattern).

Events that are not considered "device related" and will not contribute to the count of definitely-related SAEs that would trigger a Safety Evaluation Meeting.

Safety Evaluation Meeting

If safety events of potential concern occur during the trial (i.e., 3 related events or a suspicious overall pattern, as defined above) a Safety Evaluation Meeting will be triggered, and the study may be temporarily halted based on the observations. The Sponsor will inform investigators and the appropriate Regulatory Authorities in the event of any temporary halt in the study at any time during the conduct of the study. The purpose of the meeting is for investigators, the Sponsor, and the CRO Medical Monitor(s) to discuss and evaluate the safety of the subjects using available aggregated safety data.

Attendants at the Safety Evaluation Meeting will include the Program Physician of Alkahest (or his/her designee), the CRO medical monitor(s), and available active investigators participating in the trial. After sufficient data review, the Sponsor will choose one of the following courses of action:

- 1. Continue the study with no change to protocol.
- 2. Halt use of the column (all column sizes/blood-flow rates) and stop the study.
- 3. Continue with a modified protocol design and amend the protocol as appropriate.

8.6. Safety Oversight

Safety oversight will be provided by the Sponsor's Program Physician or his or her designee and the CRO's Medical Monitor(s) in concert with the site investigators. There will be no formal Data Safety Monitoring Board established. As needed, Safety Evaluation Meetings will be convened as described in Section 8.5 to monitor the ongoing safety of the study. The Sponsor's Program Physician or designee is the final authority for safety oversight in the study.

9. CLINICAL MONITORING

Clinical site monitoring is conducted to ensure that the rights and wellbeing of human subjects are protected, that the reported trial data are accurate, complete, and verifiable, and that the conduct of the trial is in compliance with the currently approved protocol/amendment(s), with GCP, and with applicable regulatory requirement(s).

- Monitoring for this study will be performed by the study CRO in accordance with the Clinical Monitoring Plan (CMP).
- Details of clinical site monitoring tasks and scope are documented in the study's CMP.
 The CMP describes in detail who will conduct monitoring, at what frequency monitoring
 will be done, at what level of detail monitoring will be performed, and the distribution of
 monitoring reports.
- Co-monitoring visits and/or independent audits may be conducted by the Sponsor in accordance with a quality oversight plan or equivalent to ensure monitoring practices are performed consistently across all participating sites and that monitors are following the CMP.

10. STATISTICAL CONSIDERATIONS

10.1. Statistical Design Model and Analytical Plans

Data from this feasibility study will be analyzed mostly in a descriptive manner. Limited statistical comparison of outcomes across the various column-size and blood-flow-rate combinations will be performed. With the limited sample size, exact methods for binomial data and t-statistics for continuous data will be used in generating 95% confidence intervals for estimates. A statistical analysis plan (SAP) will be prepared to provide details of the analysis of data. Counts and percentages of safety events will be reported separately for each combination. Similarly, continuous safety data will be summarized by combination.

No formal statistical comparison of the safety data will be performed. The rate of IDH in the general ESRD population, using the Nadir 90 definition, is 10%, based on a study in over 10,000 US patients undergoing HD (Flythe 2015). With 12 subjects there will be an approximate 70% probability of detecting at least 1 event in each week. Descriptive statistics will be utilized for trial conduct: screen failures, enrollment, withdrawal of consent, and study completion. Primary and secondary endpoints will be assessed at the beginning and end of each week of treatment for a particular column size and blood-flow rate combination. The effect of blood-flow rate will be assessed for a given column size as well as intrasubject and across-subject variability. The sample size was chosen based on clinical consideration of the study designed to test the safety and functionality of the

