10.2. Statistical Hypotheses

The primary objective of the study is to evaluate the safety and tolerability of the column when used at blood-flow rates up to 450 mL/min. The safety and tolerability will be assessed at each column size and blood-flow rate to enable comparisons across those variables in each subject (intrasubject) and across all subjects.

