10.4. Description of Statistical Methods

10.4.1. General Approach

Using the safety dataset, all safety endpoints will be summarized serially over time using descriptive statistics to assess the within-subject changes and between-condition differences. Overall baseline and demographic data will be summarized using descriptive statistics.

For analysis of the primary and secondary endpoints, the following will be considered:

- For endpoints that are continuous in nature:
 - Number of observations, mean, median, minimum and maximum, and standard deviation (SD) and change from baseline values (or percent change from baseline) will be presented as descriptive summary.
- For endpoints that are categorical in nature:
 - Frequency counts and percentages will be presented as descriptive summaries.

Subject disposition (e.g., the number of subjects enrolled, completed, and discontinued at each phase) will be summarized, and medical history data will be listed. Prior and concomitant medications taken from screening and during the study will be categorized by World Health Organization classification for therapeutic class and medication name, listed and summarized by number and percentage of subjects.

Final analyses are not limited to the summaries described herein. As noted above, analytical details and assumptions will be fully presented in the SAP.

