4.1 General Considerations

This section presents the statistical approaches that are anticipated for the analysis of the study data. These approaches may at times require modifications due to unanticipated features of the data. Deviations from analyses summarized in this document will be noted in the CSR.

All statistical analyses will be performed using SAS® Version 9.4 or higher, unless otherwise noted.

Data from this feasibility study will be analyzed mostly in a descriptive manner. Limited statistical comparison of outcomes across the various column-size and blood-flow-rate combinations will be performed. Details for any statistical tests are provided in the endpoint analysis sections (4.7, 4.8).

All safety endpoints will be summarized descriptively and tabulated as necessary, unless otherwise stated. Overall baseline and demographic data will be summarized using descriptive statistics.

For analysis of the primary and secondary endpoints, the following will be considered:

- For endpoints that are continuous in nature:
- Number of observations, mean, median, minimum and maximum, and standard deviation (SD) and change from baseline values (or percent change from baseline) will be presented as descriptive summary.
- For endpoints that are categorical in nature:
- Frequency counts and percentages will be presented as descriptive summaries.

Descriptive statistics will be utilized for trial conduct: screen failures, enrollment, withdrawal of consent, and study completion. Primary and secondary endpoints will be assessed at the beginning and end of each week of treatment for a particular column size and blood-flow rate combination. The effect of blood-flow rate will be assessed for a given column size as well as intrasubject and across-subject variability. The sample size was chosen based on clinical consideration of the study designed to test the safety and functionality of the column operated at higher blood-flow rates (up to 450 mL/min).

In general, all summary tables will be supported by a relevant subject data listing. The listings will include all data collected, and will be sorted by subject ID, and actual visit date, as applicable, unless otherwise noted. The listing will also include the column size and blood-flow rate combination as applicable.

Study day 1 is the first day of HD treatment with the day relative to the study day 1.

Statistical Analysis Plan AKST1210-101

Rev. A Page 12 of 28

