4.7 Primary Analyses

Primary analyses will evaluate safety and tolerability of the column at blood-flow rates greater than 250 mL/min in subjects with ESRD undergoing HD. Except where indicated, primary endpoints will be summarized by each column size and blood-flow rate combination (S-15 250 mL/min, S-15 up to 450 mL/min, S-25 250 mL/min, S-25 up to 450 mL/min, S-35 up to 450 mL/min) and total using both Safety and Evaluable populations.

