4.7.3 Change in Total and Free Hemoglobin

Plasma levels of total Hgb and free Hgb at baseline (i.e., the last nonmissing value prior to the start of HD with the column) and each scheduled post-baseline timepoint, along with change from baseline at each scheduled post-baseline timepoint will be summarized for the Safety, Evaluable and PP populations, by each column size and blood-flow rate combination and total.

A listing of total and free Hgb level, as well as the changes from baseline at each scheduled post-baseline timepoint will be provided.

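### The flow-rate effect within a column size is promised as a within-subject comparison, but for Hgb, Kt/V, URR and fluid balance the SAP gives only separate summaries, with no paired difference or interval

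*Protocol*

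**What the plan says.** The aim appears in several places. Protocol 10.1, repeated in SAP 4.1, states: "The effect of blood-flow rate will be assessed for a given column size as well as intrasubject and across-subject variability". Protocol 10.2, repeated in SAP 3.2, says safety and tolerability are assessed at each size and flow "to enable comparisons across those variables in each subject (intrasubject) and across all subjects". Protocol 10.4.1 says safety endpoints will be "summarized serially over time using descriptive statistics to assess the within-subject changes and between-condition differences". On intervals, protocol 10.1 says "exact methods for binomial data and t-statistics for continuous data will be used in generating 95% confidence intervals for estimates". The same section also sets a limit: "No formal statistical comparison of the safety data will be performed".

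SAP 4.1 says where the detail will be: "Details for any statistical tests are provided in the endpoint analysis sections (4.7, 4.8"). In SAP 4.7, "primary endpoints will be summarized by each column size and blood-flow rate combination". For total and free Hgb, SAP 4.7.3 gives values at baseline and at each timepoint, "along with change from baseline at each scheduled post-baseline timepoint will be summarized for the Safety, Evaluable and PP populations". That baseline is the last value before the first column treatment. SAP 4.8.1 summarizes Kt/V and URR by visit and combination, and fluid balance by combination. Neither section defines a difference between the two flow rates or mentions a confidence interval.

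**The concern.** Comparing flow rates is the purpose of the trial, and each subject serves as their own control. If the output is one column of means and SDs for 250 mL/min and another for up to 450 mL/min, the reader must subtract one mean from the other and has no valid way to attach an uncertainty to the result. The precision that the within-subject design provides is collected but not reported, and the intrasubject comparison named in protocol 10.2 is not delivered for these endpoints. In some tables the two columns may also hold different subjects, so part of the visible difference could reflect who is present and not the flow.

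**Working it through.** **1. What is planned, set against what is sampled** (protocol 15.1 to 15.3; SAP 4.7 and 4.8)

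| Outcome | Planned output | Visits giving both flows at one size | Flow contrast within a size |
|---|---|---|---|
| Total and free Hgb (4.7.3) | Values, change from pre-column baseline | V6/V9 (S-15), V18/V21 (S-35); none at S-25 | No |
| Kt/V, URR (4.8.1) | Summary by visit and combination | V6/V9, V12/V15, V18/V21 | No |
| Fluid balance (4.8.1) | Goal, actual, and gap to goal, by combination | Every session, all sizes | No |
| b2M (4.8.4) | Mixed model with flow, size and their interaction | V7/V10, V13/V16, V19/V22 | Yes |
| Other plasma proteins (4.8.6) | Mixed model, V7 versus V22, with 95% CI | None | No: S-15 at 250 versus S-35 at up to 450 |

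**2. Why two columns are not enough.** For SDs s1 and s2 and within-subject correlation ρ, the variance of the paired difference is s1² + s2² − 2ρ·s1·s2. The tables give s1 and s2 but not ρ. With both SDs equal to 1, the SD of the difference is √(2(1−ρ)): 1.00 at ρ = 0.5 and 0.45 at ρ = 0.9. The same holds for the two change-from-baseline columns.

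**3. Size.** The plan states no precision for a flow contrast, so there is no figure to reproduce. Its n of 12 follows from 15 × 0.8 = 12 (protocol 10.5). SD = 1 unit and the range of ρ are assumptions, because the documents give neither.

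- Columns treated as independent: t(22) × √(2/12) = 2.074 × 0.408 = 0.85.
- Paired: t(11) × √(2(1−ρ)/12), with t(11) = 2.201. This gives 0.64 at ρ = 0.5, 0.49 at ρ = 0.7 and 0.28 at ρ = 0.9.
- With only 8 pairs: 1.07 unpaired, against 0.84, 0.65 and 0.37 paired.

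**4. Who is in each column.** Protocol 17.1.1 makes escalation depend on IDH counts and on Hgb of at least 9 g/dL. Under 17.1.2 and 17.1.3, subjects who do not tolerate S-15 are discontinued, and those who fail on S-25 at either flow or on S-35 at 250 de-escalate. SAP 4.1 analyzes de-escalated subjects only up to that point.

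- *Safety population:* the 250 and 450 columns can differ at every size.
- *Evaluable population:* every member completed both flows for at least one size, and the order starts with S-15. The two S-15 columns therefore hold the same people, apart from missing values.
- *Above S-15:* a subject who de-escalates from S-25 or S-35 is already Evaluable, and may finish the study and enter the Per-Protocol population. The columns can therefore differ in all populations.

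**5. How much this could bias Hgb.** Assume normal Hgb with SD 1 g/dL, correlation 0.8 between the two flow visits, no true flow effect, entry only at Hgb of 9.0 or more (exclusion criterion 15), and escalation only if the 250 value is at least 9. With baseline also correlated 0.8, the raw 450 column exceeds the raw 250 column by about 0.05 g/dL (mean 10.5) or 0.08 g/dL (mean 10.0). If baseline is correlated only 0.6, the excess at mean 10.0 is about 0.14. In the change-from-baseline columns, which the SAP also tabulates, the excess is about 0.01 to 0.07 over the same settings. The paired difference is not free of selection either, at about −0.02 to −0.04.

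**The case against.** The strongest reply is that protocol 10.1 limits itself: safety data get no formal comparison, SAP 3.2 calls the study primarily descriptive, and in the quoted sentence of 10.1 the word intrasubject is attached to variability. This stands to the extent that no hypothesis test is missing. It does not answer protocol 10.2, 10.4.1 and SAP 3.2, which speak of comparison within subjects and between conditions. A descriptive paired mean with an interval also fits the t-based intervals that 10.1 itself announces.

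A second reply is that listings show each subject's values, so with about 12 subjects the pairs can be read off. That is true, but a difference derived afterwards from listings is not a planned summary.

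A third is that paired differences would not be clean. This is correct. Flow always runs low to high, and session length is planned to change with it (about 4 to 6 hours at 250 mL/min and 3 to 4 hours at up to 450 mL/min), so the table must say so. Nor would it cover IDH; the point is limited to the continuous measures.

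A reader might also infer that the change of subjects between columns hides Hgb loss at high flow. The documents do not support that. Entry requires Hgb of at least 9.0 g/dL, change from baseline is tabulated, the Evaluable S-15 columns match, and SAP 4.7.4 counts de-escalations by reason, including anemia, as well as discontinuations. Nor does the SAP merely tabulate everything outside b2M: section 4.8.6 models other proteins, though its V7 versus V22 contrast mixes flow with column size.

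**Conclusion.** The gap is real and modest. For Hgb, Kt/V, URR and fluid balance, the SAP specifies no within-subject flow difference at a given column size and no measure of its uncertainty, although the plan says such comparisons are the aim. What is lost is precision: at n = 12 the half-width is 0.85 SD from separate columns, against 0.64 to 0.28 SD paired for correlations of 0.5 to 0.9. The gain depends on SD and correlation values that the documents do not give, and on how many pairs remain. Different membership of the columns is a secondary matter, confined to the Safety tables and to sizes above S-15. Any resulting Hgb bias is probably small, especially in change from baseline. Nothing here invalidates the planned summaries, but the addition should be made because it is cheap and answers the trial's own question.

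**What to change.** In SAP 4.7.3 and 4.8.1, add for each column size with both flows sampled, among subjects with both values, the within-subject difference (up to 450 minus 250). Report number of pairs, mean, SD and paired t-based 95% CI, labelled descriptive and without a test:

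- total and free Hgb: V9 − V6 and V21 − V18;
- Kt/V and URR: V9 − V6, V15 − V12 and V21 − V18;
- mean fluid removed per session: each column size.

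Beside each, give the number of subjects with a 250 value but no 450 value, and their 250 mean. Add a footnote that the difference includes any week effect because the order is fixed and, for Kt/V, URR and fluid removal, the planned change in session length. At the same time, reconcile the list of combinations in SAP 4.7, which omits S-35 at 250 mL/min, with SAP 4.8, which includes it; the S-35 Hgb pair needs that column.

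The cost is SAP wording and one or two tables from data already scheduled, with no extra sampling or subjects. The small downside is that subjects without a pair are shown separately.

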10.2. Statistical Hypotheses

The primary objective of the study is to evaluate the safety and tolerability of the column when used at blood-flow rates up to 450 mL/min. The safety and tolerability will be assessed at each column size and blood-flow rate to enable comparisons across those variables in each subject (intrasubject) and across all subjects.

10.3. Analysis Datasets

Two (2) analysis datasets will be defined as follows:

- Safety Dataset: all subjects who received at least 1 (or partial) HD treatment with the column.
- Evaluable Dataset: all subjects who complete blood-flow rates up to 450 mL/min for at least 1 column size (e.g., S-15 at 250 and up to 450 mL/min).

The presentation of baseline characteristics will be conducted on the Safety Dataset. Comparison of the safety and tolerability of each column size and blood-flow rate will use both the Safety Dataset and Evaluable Dataset.

10.4. Description of Statistical Methods

10.4.1. General Approach

Using the safety dataset, all safety endpoints will be summarized serially over time using descriptive statistics to assess the within-subject changes and between-condition differences. Overall baseline and demographic data will be summarized using descriptive statistics.

For analysis of the primary and secondary endpoints, the following will be considered:

- For endpoints that are continuous in nature:
 - Number of observations, mean, median, minimum and maximum, and standard deviation (SD) and change from baseline values (or percent change from baseline) will be presented as descriptive summary.
- For endpoints that are categorical in nature:
 - Frequency counts and percentages will be presented as descriptive summaries.

Subject disposition (e.g., the number of subjects enrolled, completed, and discontinued at each phase) will be summarized, and medical history data will be listed. Prior and concomitant medications taken from screening and during the study will be categorized by World Health Organization classification for therapeutic class and medication name, listed and summarized by number and percentage of subjects.

Final analyses are not limited to the summaries described herein. As noted above, analytical details and assumptions will be fully presented in the SAP.

10.4.2. Analysis of the Primary Endpoint

Safety and tolerability will be evaluated by examining the occurrence of TEAEs and AEs leading to de-escalation and/or discontinuation from the study and by the number of subjects who are able to complete each phase (i.e., a column size at both blood-flow rates).

Summary tabulations of the reported AEs will be presented by column size after the verbatim terms have been coded to preferred terms (PTs) and system organ classes (SOCs) using the MedDRA Version 23.0 coding dictionary or higher. The summaries will include severity and attribution to the study device. Multiple reports of the same AE by the same subject will be counted only once at the highest severity and strongest attribution to the study device.

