8.4. Reporting Procedures

8.4.1. Adverse Event Reporting

All subjects who have given informed consent will be evaluated for AEs. All AEs that occur after initiation of treatment with the column will be considered TEAEs. Subjects with TEAEs must be followed until the AE/ADE is resolved or is stable, unless the subject is lost to follow up.

Each AE/ADE must be described as follows: the date of onset, date of resolution, severity (mild, moderate, severe), frequency of the event (single episode, intermittent, continuous), action taken with study device (no action taken, device discontinued), outcome, relationship to study device* (unrelated, possibly related, definitely related), and seriousness criteria. Each AE/ADE must be recorded separately.

*Note: Assessment of the relationship to study device will be made only when the AE occurs after the subject has initiated at least one (1) treatment with the column. An AE occurring before the subject's exposure to the column will always be labeled as "unrelated."

Any AE/ADE or SAE/SADE occurring during the study must be documented in the subject's source documentation and as an AE/ADE in the CRF. All SAE/SADEs should be reported to the Sponsor according to the reporting timeframes specified in Section 8.4.2.1.

[figure not shown]
The investigator should attempt to establish a diagnosis of the event (that meets the definition of an AE/ADE or SAE/SADE) based on signs, symptoms, and/or other clinical information. In such cases, the diagnosis should be documented as the AE/ADE and/or SAE/SADE and not the individual signs or symptoms. The diagnosis will become the basis for the verbatim term as reported by the investigator. If no diagnosis is known and clinical signs and symptoms are not present, the abnormal finding should be recorded.

In addition to the investigator's own description of the AE/ADE, each AE/ADE will be encoded according to the Medical Dictionary for Regulatory Activities (MedDRA). The investigator will take all appropriate and necessary therapeutic measures required for resolution of and AE/ADE. Any medication necessary for the treatment of an AE/ADE must be recorded on the concomitant medication CRF.

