17.1.2. De-escalation Rules

The purpose of the de-escalation rules is to ensure the safety of a subject who is experiencing IDH, anemia or other safety issues that may be related to the column size.

A subject should be de-escalated if during the 1-week treatment period they experience the number of IDH events described in the table above and/or have an Hgb level < 9 g/dL despite receiving optimized treatment with ESA.

De-escalation will only be applicable at V11 through V19 as shown in Figure 4 below. Subjects who do not tolerate treatment with the S-15 column at any time prior to V11 or after V19 will be discontinued (see Section 17.1.13. Discontinuation Rules).

Figure 4. De-escalation Schematic

Subjects will continue with the same visit schedule after de-escalation. At the visit following confirmation of de-escalation, treatment will resume with the previous column size at the high flow rate (up to 450 mL/min).

- ➤ If de-escalation occurs during V11 through V16, subjects will resume treatment at the next scheduled visit with the S-15 column at up to 450 mL/min and will continue with this column size/flow rate combination through EOT (V22).
- ➤ If de-escalation occurs during V17 through V19, subjects will resume treatment at the next scheduled visit with the S-25 column at up to 450 mL/min and will continue with this column size/flow rate combination through EOT (V22).

Table 4 below illustrates the visit schedule for subjects who de-escalate. *Note*: the only change compared to Section 15 is column size and flow rate.

Table 4. Schedule of Events for Subjects Who De-escalate

					,	Treatm	ent Peri	iod					EOS
Visit Number	V11	V12	V13	V14	V15	V16	V17	V18	V19	V20	V21	V22 (EOT)	V23
Study Week		Week 3			Week 4	ļ	,	Week 5			Week	6	Week 7
Study Day(s) (± 1)	Day 15	Day 17	Day 20	Day 22	Day 24	Day 27	Day 29	Day 31	Day 34	Day 36	Day 38	Day 41	Day 43
Procedure													
Physical examination													X
12-lead ECG													X
Targeted physical examination	X	X	X	X	X	X	X	X	X	X	X	X	
Weight	X	X	X	X	X	X	X	X	X	X	X	X	X
Vital signs ¹	X	X	X	X	X	X	X	X	X	X	X	X	X
Laboratory tests ²		X	X		X	X	X	X	X	X		X	X
Column size			S-	15			S-15	OR S-2	.5 (if de	e-escala	ated aft	er V16)	
Hemodialysis blood-flow rate (mL/min)						Up	to 450						
Assessment of fluid status	X	X	X	X	X	X	X	X	X	X	X	X	
Kt/V assessment		X			X		_	X			X	X	_
Adverse events and concomitant medications	X	X	X	X	X	X	X	X	X	X	X	X	X

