17.1.3. Discontinuation Rules

Subjects will be discontinued and complete the End of Study visit procedures if:

- Subject does not tolerate the S-15 column at either flow rate
- Subject does not tolerate the S-35 at the higher flow rate (up to 450 mL/min)
- Subject has already de-escalated and they experience the number of IDH events described in the Table 3 and/or have an Hgb level < 9 g/dL despite receiving optimized treatment with ESA
- At any time during the study at the investigator's discretion

As a reminder, all occurrences of IDH after the time of consent will be recorded as AEs.

^{2.} For additional information, see Section 15.3 Schedule of Laboratory Tests.

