4.7.1 Adverse Events

All treatment emergent adverse events (TEAEs) will be reported. A TEAE is defined as an AE that occurs on or after the date of the first column use.

A summary of all TEAEs, as reported in the EDC, by the number and percentages of subjects who experienced any of the following will be provided for the Safety population:

- Any TEAE, including severity (Mild, Moderate, and Severe), relationship to study device and procedures (Unrelated, Possibly Related, Definitively Related), TEAEs leading to discontinuation of study participation.
- Any serious adverse events (SAEs), including severity (Mild, Moderate, and Severe), relationship to study device and procedures (Unrelated, Possibly Related, Definitively Related), SAEs leading to discontinuation of study participation
- Any ADEs, including severity (Mild, Moderate, and Severe), relationship to study procedures (Unrelated, Possibly Related, Definitively Related), ADEs leading to discontinuation of study participation
- Any fatal TEAEs, including relationship to study device and procedures (Unrelated, Possibly Related, Definitively Related)

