4.7.4 Tolerability of each Column Size and Blood-flow-rate Combination

The number and percentage of subjects will be summarized for the Safety, Evaluable and PP populations, by each column size and blood-flow rate combination and total for the following:

- Subjects entered each column size/blood-flowrate combination
- Subjects who de-escalated to a lower column size categorized by reason: IDH, anemia, or other. Anemia (as it pertains to de-escalation) is defined as having an Hgb lab value of < 9 g/dL despite receiving optimized treatment with erythropoietin stimulating agents (ESA).
- Subjects who were discontinued due to safety, tolerability, and/or investigator discretion
- Subjects who completed all the visits

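### AEs leading to de-escalation are part of the protocol's primary analysis, but the AE action-taken field has no value for them and SAP 4.7.1 has no row

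*Protocol*

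**What the plan says.** Protocol 10.4.2 sets out the primary analysis: "Safety and tolerability will be evaluated by examining the occurrence of TEAEs and AEs leading to de-escalation and/or discontinuation from the study". It adds the number of subjects completing each phase, and asks that the AE summaries include severity and attribution to the device. Protocol 10.4.1 leaves the analytical details to the SAP.

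Protocol 8.4.1 lists the attributes that every AE must carry. One is "action taken with study device (no action taken, device discontinued"; no third value is given.

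SAP 4.7.1 tabulates "TEAEs leading to discontinuation of study participation", the same for SAEs, and "ADEs leading to discontinuation of study participation". The SOC/PT tables in SAP 4.7.1.1, 4.7.1.2 and 4.7.1.4 split by severity and relationship. None splits by de-escalation, and the only flag named for the AE listing is TEAE status.

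SAP 4.7.4, also a primary analysis, counts "Subjects who de-escalated to a lower column size categorized by reason: IDH, anemia, or other", and does so "by each column size and blood-flow rate combination and total for the following".

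Protocol 17.1.2 says de-escalation is for subjects with "IDH, anemia or other safety issues that may be related to the column size". A de-escalated subject resumes on the previous column size at the high flow rate and stays on it through the end of treatment.

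**The concern.** De-escalation is how a subject can fail to tolerate a combination and still remain in the study. The protocol recognises this by naming it beside discontinuation in the primary analysis. The SAP carries only discontinuation into the AE tables, and the prescribed AE attribute has no code from which the other half could be built.

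At stake is the comparison of combinations, which Protocol 10.2 and SAP 3.2 give as the purpose of the assessment. If an AE that stops a subject on one column is displayed as treatment-limiting and an AE that stops a subject on another column is not, the rows are not comparable across columns. For an investigational device, whether the event behind a de-escalation was device-related, and how severe it was, is a question the safety report should answer from a specified table.

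**Working it through.** The plan states no figure on this point, so the check is a comparison of text.

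**Step 1: can the AE field record de-escalation?** Protocol 8.4.1 offers no action or device discontinued. Under Protocol 17.1.2 the subject continues on a smaller column. Something was done, so the first value does not fit. The device is still in use, so the second does not fit either.

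**Step 2: does the SAP ask for the result?** SAP 4.7.1 and its subsections give incidence, SOC/PT, severity, relationship and discontinuation of participation. There is no summary of AEs leading to de-escalation.

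**Step 3: which combinations are affected?** The rules in Protocol 17.1.2 and 17.1.3 for a first intolerance give:

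| Combination | Week, visits | Consequence of intolerance | Leading-to row in SAP 4.7.1 |
|---|---|---|---|
| S-15, 250 mL/min | 1, V5–V7 | Discontinued | Yes |
| S-15, up to 450 | 2, V8–V10 | Discontinued | Yes |
| S-25, 250 | 3, V11–V13 | De-escalated to S-15 | None |
| S-25, up to 450 | 4, V14–V16 | De-escalated to S-15 | None |
| S-35, 250 | 5, V17–V19 | De-escalated to S-25 | None |
| S-35, up to 450 | 6, V20–V22 | Discontinued | Yes |

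The gap covers 3 of 6 combinations, or 9 of the 18 column visits (V11–V19 out of V5–V22). An investigator may discontinue a subject at any time, and such a case reaches a row in any combination. The table describes what the IDH and hemoglobin rules produce.

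**Step 4: what does SAP 4.7.4 recover?**
- *Reason IDH.* The event type is known. Protocol 17.1.3 says "all occurrences of IDH after the time of consent will be recorded as AEs", and SAP 4.7.2 tabulates IDH counts by combination. The severity and relatedness of the particular events that led to de-escalation are not tabulated.
- *Reason anemia.* Hemoglobin is summarised by combination in SAP 4.7.3, and Protocol 7.2 records clinically significant laboratory values as AEs. The position is similar.
- *Reason other.* The table gives a count and nothing more: no preferred term, severity or relatedness.

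**Step 5: does anything else in the analysis compensate?** SAP 4.1 includes de-escalated subjects only up to the point of de-escalation. The triggering AE is therefore among the last evidence on that combination to enter the analysis, which makes its identification more important.

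**The case against.** The strongest reply is that little is lost. An AE that precedes de-escalation is still a TEAE, counted with its preferred term, worst severity and attribution, and included in the listing of all AEs. De-escalation itself is tabulated as a primary analysis in SAP 4.7.4, by reason and combination, in three populations. The protocol speaks of examining occurrence and does not prescribe a particular row. For IDH the trigger is a weekly count over a limit, so a subject-level reason suits it at least as well as a code on a single AE. All of this stands. It confines the loss mainly to de-escalations for other reasons, and to the link between event and consequence.

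It does not remove the point. The protocol names AEs leading to de-escalation as something to be analysed, and a count of subjects in three reason categories is not an analysis of those AEs.

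A reader might infer more than the documents support:

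- *That these AEs disappear or are coded wrongly.* They remain in the TEAE tables. The CRF and the table and listing shells are not in the documents. SAP 4.7.4 presupposes a recorded reason for de-escalation, so a separate record may well exist.
- *That the AE tables would show these events as needing no action and so understate the safety result.* No SAP table summarises action taken. Incidence, severity and relatedness overall are unaffected.
- *That S-35 at up to 450 mL/min is affected.* Intolerance there leads to discontinuation, which is tabulated.
- *That AEs leading to a lower flow rate or an early end of a session are also wrongly omitted.* Protocol 10.4.2 does not promise them. Protocol 7.1.1.1.6 captures reasons for flow changes at each session, and the listing in SAP 4.9.3 links low SBP to flow changes and stopped sessions.

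**Conclusion.** The plan is wrong as written on this point, within narrow limits. A component of the primary analysis stated in the protocol has no matching value in the prescribed AE field and no output in the SAP. The consequence is that AEs causing de-escalation on S-25 at either flow, or on S-35 at 250 mL/min, cannot be identified as treatment-limiting by preferred term, severity and relatedness. For S-15 and for S-35 at up to 450 mL/min, AEs that end participation are so identified.

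The size is three of six combinations, chiefly for de-escalations with reason other. No percentage of subjects can be given, because the documents contain no expected de-escalation rate and no split by reason. The gap does not affect the sample size or any clinical rule.

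The conclusion assumes that the AE form follows the two-value list in Protocol 8.4.1, and that the table and listing shells add nothing beyond the SAP text. If the form or shells already carry a de-escalation item, what remains is to bring the protocol and SAP text into line with them.

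**What to change.** 1. In Protocol 8.4.1 and the AE form, add a third action-taken value, *column size reduced (de-escalated)*, with a line of completion guidance.
2. In SAP 4.7.1, add TEAEs and ADEs leading to de-escalation by SOC/PT, severity, relatedness and combination, cross-referenced to the reasons in SAP 4.7.4 so that the two displays can be reconciled. Carry the same flag in the AE listing.
3. Name all six combinations for these rows. The list in SAP 4.7 leaves out S-35 at 250 mL/min, where de-escalation can occur; the list in SAP 4.8 includes it.
4. If data are already collected, derive the flag by linking AE onset to the de-escalation record, and state the linking rule in the SAP. For IDH, the rule should flag all events in the week that exceeded the limit, since no single event is the trigger.

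The cost is one option on a form, short guidance, and one added summary with its flag. Under item 4 it is a programming rule and no new data collection, provided the de-escalation record that SAP 4.7.4 presupposes exists. Flow-reduction or early-session-end rows may be added if the sponsor wants them, but they are not needed to correct this error.
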